If the pilot study finishes without violating any stop rules and without any serious adverse events the second part of the study will be initiated. This will be conducted as a phase 2 study where 24 patients with histologically verified or clinically suspicious sigmoid colon cancer and rectal cancer will be included. Patients will be recruited from the Department of Surgery, Zealand University Hospital, Department of Surgery, Slagelse Sygehus and Department of Surgery, Sydvestjysk Sygehus after their case has been reviewed by the multidisciplinary team (MDT). Standard treatment involves intended curative surgery within two weeks after the diagnosis. The treatment will be performed within a few days and it will be ensured that the experimental treatment will not lead to a significant delay of intended curative surgery.

In relation to both parts of the study following samples will be collected:

Blood samples will be collected prior to the treatment with intratumoral influenza vaccine. Furthermore, blood samples will be collected on admission prior to elective surgery, within 3 days after surgery, and when the patients return to the outpatient clinic (approximately 14 days after surgery). The systemic response to intratumoral influenza vaccine will be evaluated through a multiplex gene assay, multiplex cytokine analysis, flow cytometry and NK cell activity analysis. Furthermore, ct/cfDNA will be analyzed and cell adhesion assays will be performed.

In relation to the intervention, eight intraluminal biopsies (8 x 0.5-1.5 cm) from the tumor will be collected and stored in a biobank for later analysis. The samples will be collected just before influenza vaccine is injected. In order to ensure uniformity, all tumor biopsy analyses will be performed when samples have been obtained from all participants. Tumor tissue will be registered and stored in "Dansk Cancer Biobank" according to Danish law. The Biobank will be approved by the Danish Data Protection Agency and subjected to "Persondataloven". An additional approval will be required for future research with remaining tumor

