Adverse events / reactions are recorded from day of treatment (Day 0) until the surgery, as it will be difficult to differ between adverse events/reactions to the experimental treatment or surgery. All adverse events / reactions should be described in medical terminology in the patient's file and recorded in case report forms (CRF). The following information must be recorded: start date/date when observed, severity, any initiated treatment, assessment of the AE if it meets the criteria for SAE, end date, and relationship to study drug. For AEs that meet the criteria for SAE, the outcome must be recorded.

The adverse reactions are classified according to CTCAE version 4.0 (Common Terminology Criteria for Adverse Events)

Reporting adverse events

Unexpected and serious suspected adverse reactions that are fatal or life-threatening shall be reported to the Medical Products Agency and Science Ethics Committee as soon as possible, and no later than 7 days after the sponsor has knowledge of such suspected side effect. Within 8 days after reporting, the sponsor must notify the National Board of Health and Ethics Committee with all relevant information on the sponsor and the investigator's follow-up report.

All other unexpected serious suspected adverse reactions should be reported to the same authorities within 15 days after the sponsor has been informed of this. Any report must be accompanied by comments on any consequences for the trial. After completion of the trial, all adverse reactions will be reported in the final report to the Board of Health and Ethics Committee.

Sponsor must report all events related to the medical device to the manufacturer.

Definitions

- Adverse Event, AE: Any adverse events in a patient that occur or worsen during the trial and does
 not necessarily have a causal relationship to study treatments.
- Adverse Reaction, AR: All noxious and unintended reactions to a trial drug at any dose. The term
 "reaction to a trial drug" means that a possible relation between the study drug and the adverse
 reaction cannot be excluded.
- Unexpected Adverse Reaction, UAR: An adverse reaction with a nature or severity that is not in accordance with the current product information.
- Serious Adverse Event, SAE or Serious Adverse Reaction, SAR: an event or side effect that at any
 dose:
 - Results in death.
 - Is life threatening.
 - Leads to hospitalization or prolongation of hospital stay.

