 - Results in persistent or significant disability or incapacity.
 - Leads to a congenital anomaly or birth defect.
 - Is a major medical event.
- Suspected Unexpected Serious Adverse Reactions, SUSARs: Unexpected and serious suspected
 adverse reactions that are not described in the product information for the experimental drug.

The investigator must, based on medical and scientific experience, assess whether it is relevant to report the medical event /reaction that is not immediately life-threatening, but which may bring the patient's health at risk or require medical treatment, to prevent one of the above mentioned events/reactions. Such incidents should usually be classified as serious.

Other events to be treated as serious adverse events

If the patient becomes pregnant around the time of treatment or 6 months after treatment, she must immediately be removed from the trial. The patient should be followed throughout the pregnancy. The results of pregnancy and childbirth must be reported, even if the process is normal and without AEs.

Stop rules

If a patient previously treated with influenza vaccine experiences anaphylactic shock to the intratumoral application of influenza vaccine the study will be stopped immediately. If a perforation of the bowel happens at the intervention site eg. at tumor level but not in the remaining bowel, as this will be seen as a known side effect to colonoscopies. Additionally, the trial may be interrupted prematurely and before inclusion of all patients if:

- Unexpected, significant or unacceptable risks to patients.
- Failure to enter patients at an acceptable rate.
- Insufficient adherence to protocol requirements
- Unacceptable compliance.
- Decision by sponsor or regulatory authority based on safety evidence.

Side effects to the influenza vaccine

Very common (> 10%)	Decreased appetite, reactions and discomfort at the insertion site, malaise. Myalgia. Headache, Irritability.
Common (1-10%)	Fever, chills.
Uncommon (0.1-1%)	Abdominal pain. Lymphadenopathy, Thrombocytopenia. Dizziness.
Rare (0.01-0.1%)	Dyspnea. Arthralgia.

Paresthesia.
Allergic reactions, Hypersensitivity.

Side effects to applying the influenza vaccine intratumorally using a needle in the colon.

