Injecting a needle into a tumor or normal tissue in the colon is part of many routine clinical procedures. Every patient with an endoscopically identified malignant polyp or tumor will be marked by injecting ink by a needle in the adjacent tissue⁹, so that part can be identified during the subsequent surgery. This techniques has been used since the 1980's and has virtually no both short term and long term side effects⁹. Injecting a needle and administering up to 10 ml of saline is also a routine part of endoscopic mucosal resection¹⁰.

Side effects to the additional endoscopy

The study necessitates and additional endoscopy of the sigmoid colon. This is associated with the same risk as in a standard endoscopy of the sigmoid colon, ie. a risk of bleeding, infection and perforation of the colon, up to 0.5% overall. These complications are severe and will require hospitalization and presumably surgery. Prior to the endoscopy, the included patient will have to take a laxative to cleanse the bowel. This may be associated with discomfort.

7. Biological material from participants

Blood samples

Blood samples will be collected four times during the study period. Before intratumoral influenza vaccine treatment (baseline), on admission to surgery, within 72 hours after the surgical procedure, and when patients return to the outpatient clinic for final evaluation (approximately 14 days surgery). Additionally, one blood sample will be collected at baseline and prior to surgery for flow analysis.

Following blood samples will be collected at four specific time points:

- 1 x 6 ml in serum separator tubes
- 5 x 10 ml in EDTA tubes for full blood, buffy coat, flow cytometry, NK cell activity and ct/cfDNA
- 2 x 2.5 ml in PAXgene RNA tubes

A total of 244 ml will be collected during the entire study period.

Systemic immunological responses will be analyzed when all samples have been collected from all patients. Research shows that immune cells and their invasion of the primary tumor correlate to the patient's prognosis, again suggesting that the immune response is important for cancer growth^{11–13}, thus we will perform an evaluation of the systemic immunologic response.

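### The perforation stop rule states no consequence, and perforation away from the tumour is not reconciled with the condition for opening phase 2

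*Protocol*

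**What the plan says.** Four places in the protocol bear on this.

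- **Section 6, Stop rules.** The first rule concerns a previously vaccinated patient who "experiences anaphylactic shock to the intratumoral application of influenza vaccine the study will be stopped immediately". The next sentence reads "If a perforation of the bowel happens at the intervention site eg. at tumor level but not in the remaining bowel", continues "as this will be seen as a known side effect to colonoscopies", and stops there. A list of general grounds on which the trial may be interrupted follows.
- **Section 3, Study design.** The condition for expanding from six to 24 further patients is: "If the pilot study finishes without violating any stop rules and without any serious adverse events the second part of the study will be initiated".
- **Section 6, Side effects to the additional endoscopy.** Bleeding, infection and perforation together are put at up to 0.5%, and the protocol adds: "These complications are severe and will require hospitalization and presumably surgery".
- **Section 6, Definitions.** One criterion for a serious adverse event is that it "Leads to hospitalization or prolongation of hospital stay". An adverse event need not be caused by the study treatment.

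**The concern.** The primary objective is safety, and section 4 says that safety will be judged by reading the reports, not by statistical analysis. The written stop rules therefore carry much of the protection. Perforation at the injection site is the one event specific to the injection procedure that the protocol singles out for a stop rule, and that rule has a condition and a reason but no action.

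A second gap concerns perforation away from the tumour. The stop rule seems to set it aside as a recognised complication of colonoscopy, but the condition for opening phase 2 makes no such allowance. If it happened in a pilot patient, the investigators would have to work out for themselves how the two provisions combine, with the event already known.

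**Working it through.** The protocol has no design figure to reproduce here; section 4 says that no formal sample size calculation was possible. The check is mainly a comparison of texts.

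**Step 1: is the perforation sentence complete?** The anaphylaxis sentence has a condition and a consequence (the study stops). The perforation sentence has a condition (at the tumour, not elsewhere) and a reason (recognised with colonoscopy), then a full stop. Nothing marks a redaction. The likely meaning is that perforation at the tumour stops the study and perforation elsewhere does not, but this comes from the neighbouring sentence and not from the rule itself. The pronoun in the reason is also loose: grammatically it could attach to the tumour-site event, which would reverse the meaning.

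**Step 2: is a perforation a serious adverse event?** Adverse events are recorded from Day 0 until surgery, so one arising at the study endoscopy is captured. The protocol says that these complications require hospital admission, and admission is a seriousness criterion whatever the cause. So yes, at either site.

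**Step 3: put the two decisions side by side.**

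| Event | Stop rules (section 6) | Opening of phase 2 (section 3) |
|---|---|---|
| Pilot, perforation at the tumour | Condition stated, no consequence | Condition not met |
| Pilot, perforation elsewhere | Apparently exempt | Condition not met |
| 24-patient part, perforation at the tumour | Condition stated, no consequence; general grounds only | Does not apply |
| 24-patient part, perforation elsewhere | Apparently exempt; general grounds only | Does not apply |

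The incomplete sentence affects both parts of the study. The mismatch between exemption and blocking arises only in the second row. There the study is not stopped, yet the condition for phase 2 has already failed, and nothing says whether the pilot patients still to come may be treated.

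**Step 4: how often could the second row occur?**

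- Inputs: n = 6 pilot patients (sections 3 and 5); p = 0.005, the protocol's upper figure for bleeding, infection and perforation combined (section 6).
- Formula: probability of at least one event = 1 − (1 − p)^n.
- Result: 1 − 0.995^6 = 1 − 0.9704 = 0.0296, or 3.0%.

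At the protocol's ceiling this is an upper bound for perforation away from the tumour, because 0.5% covers three complications. If the combined risk were instead anywhere from 0.1% to 1% (an assumed range), the result would run from 0.6% to 5.9%. The protocol gives no separate risk for perforation at the tumour after injection, so the frequency of that event cannot be calculated.

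**The case against.** The strongest reply is that stopping a study and expanding it are separate decisions. The phase 2 condition joins two requirements: no breach of a stop rule, and no serious adverse event. Both provisions can be applied literally, and it is coherent to ask more before expanding than before continuing. This stands. A reader might infer that the two rules contradict each other; they do not. They are unreconciled.

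It also stands that the event which is both exempt and blocking is perforation in the remaining bowel of a pilot patient, not the tumour-site perforation named in the incomplete sentence. Nor is the phase 2 condition vague about causality: it covers any serious adverse event, and the definition does not require a causal link. In the pilot, a perforation at either site therefore fails that condition whatever the incomplete sentence was meant to say.

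A reader might further infer that the 24-patient part has no safeguard. The text does not support that. Section 3 (Safety endpoints) provides for continuous review and for a hold if safety becomes unacceptable, and the Stop rules allow interruption for unacceptable risk or by decision of the sponsor or an authority. These provisions are discretionary, but they exist.

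A reader might also suspect that the anaphylaxis rule cannot be applied because vaccination history is not collected. The itemised data in section 8 are those taken from health records, not the case report form, which is not shown. The eligibility criteria already ask about recent influenza vaccination and past allergic reaction to it.

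None of this supplies the missing consequence. Discretionary grounds do not replace a specific rule that the protocol evidently set out to write, and inference from the sentence before is a weak basis for a stop rule.

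**Conclusion.** Wrong as written. The perforation stop rule names no action and cannot be followed without guessing its intent. This rests on the text alone and needs no assumption.

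The second part is narrower. In the six-patient pilot, perforation away from the tumour appears exempt from stopping yet prevents phase 2 from opening, and the protocol is silent on how these combine and on the remaining pilot patients. It assumes that the sentence does mean to exempt that event, which is the natural reading, and that admission follows, as the protocol itself says. Its chance is at most 3.0% at the protocol's ceiling.

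Larger figures are tempting but do not measure this defect. Pooling all 30 patients gives 1 − 0.995^30 = 14.0%, but the mismatch exists only in the pilot. Calculations of how often unrelated serious events would block phase 2 need rates that the protocol does not give, and they describe the strictness of that condition, not the gap in the perforation rule.

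**What to change.** Complete the perforation sentence in the Stop rules with its consequence, so that it can be read without reference to the sentence before it. Then reconcile the Stop rules, the Study design condition in section 3 and the endoscopy risk text in section 6. The effect of a perforation at the tumour, and of one elsewhere in the bowel, should be explicit both for stopping the study and for opening phase 2. The two effects may differ, provided that each is stated. The text should also say whether the remaining pilot patients may be treated once the condition for phase 2 has failed.

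The clinical content of these rules is for the sponsor and the authorities to settle. The cost is one short protocol amendment, with no extra patients.
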